Protocol & SAP

Airways to Alteration (A2A): Investigating the Impact of Breathwork & Meditation on Conscious State (NCT06916312)

Comparing Effects of Intense Breathwork to Meditation on Altered States of Consciousness (A2A)

Summary

This study aims to investigate the impact of high ventilation breathwork (HVB) and meditation on altered states of consciousness (ASCs). The study will compare the effects of a single guided HVB session to a single guided body scan meditation session. The primary aim is to explore the impact of HVB and meditation on ASCs, while secondary aims relate to mental health and wellbeing.

[name]

Original document date: May 21, 2025

Edited document data: June 09, 2025

Reason for edit: Had EBI listed as secondary outcome measure (incorrect) in the Protocol instead of a primary outcome measure (correct) as per the pre-registration NCT06916312.

Abstract

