Principal research questions/objectives include: 1. Investigate potential differences in ASCs induced by a single session of HVB—in particular Conscious Connected Breathing (CCB)—versus a body scan meditation. 2. Examine whether HVB (CCB) induces ASCs comparable to psychedelics (via the Altered States Database, an open-science project based on systematic literature reviews). 3. Investigate potential differences on mental health and wellbeing after HVB or a body scan meditation. 4. Examine correlation between ASCs and changes on mental health and wellbeing, in addition to the relationship between preparedness/predictiveness of participants to experience psychedelic effects and ASCs.

Materials/Methods

Unlike slow breathwork, high ventilation breathwork (HVB) has not been exposed to the same level of robust clinical testing to date [2,6-8], a necessary step to realise its potential application as a therapeutic modality. We will conduct the first randomised-controlled trial (RCT) of HVB on altered states of consciousness (ASCs). This will take the form of a small pilot study wherein participants are randomised to in-person, guided HVB or a meditation group.

Study type

This will be an experimental study, where participants are randomly assigned to a HVB intervention or body scan meditation. This will be a small-scale pilot RCT, hopefully leading to a large-scale clinical trial in the future (depending on funding).

Data collection procedures

Quantitative data: The primary outcomes will be ASCs as measured by the Five Dimension ASC Rating Scale (5D-ASC) [9], the short Mystical Experience Questionnaire (MEQ) [10], and Emotional Breakthrough Inventory (EBI) [11].

Secondary outcomes include: the Psychological Insight Questionnaire (PIQ) [12], Depression Anxiety Stress Scales (DASS) [13], Short Warwick-Edinburgh Mental Wellbeing Scale (SWEMWBS) [14], Imperial Psychedelic Predictor Scale (IPPS) [15], PROMIS Sleep-Related Impairment Scale (PROMIS-4a) [16], Shortened Fatigue Questionnaire (SFQ) [17], and Cambridge Depersonalisation Scale-State Version (CDSS) [18].

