There will also be optional open-ended responses on overall experience of the meditation or breathwork. The following state measures will be completed immediately after the HVB and meditation sessions: 5D-ASC, MEQ, EBI and CDSS. The following trait measures will be completed 7-10 days before and 7-10 days after the breathwork and meditation sessions: DASS, SWEMWBS, PROMIS and SFQ. The IPPS will be completed when subjects consent to participating, and the PIQ will be completed 7-10 days after the breathwork and meditation sessions.

Qualitative data: Optional open-ended responses will capture participants' lived experiences after the breathwork and meditation sessions.

Sample

Given this is a small pilot study, 24 participants (12 per group) will be recruited. The studies of Bahi et al. (2023) and Havenith et al. (2024) report HVB having comparable effects on ASCs to moderate-high doses of psilocybin, which has large-very large effect sizes on ASCs. This is an ethical number of participants for a single session HVB intervention with two breathwork facilitators present. It is ideal to have no more than six breathworkers per facilitator.

Accordingly, there will be two groups of 12 for our study (12 in the HVB group, and 12 in the meditation group). At 80% power with an alpha of 0.05, based on Havenith et al.'s HVB study's between-groups effect size (1.29) on the self-completion depressive symptomology survey, a sample size of 22 is needed, allowing room for potential attrition. Effect sizes reported by Bahi et al. were greater, but this was a within-groups design.

Participants will be recruited from the local area using advertisements online (social media/email) via the PI and (co)facilitators' networks. It will be incumbent upon those people interested in taking part to contact the PI. Participants will be comprehensively screened and the inclusion criteria will be adults with experience of HVB, living in Brighton (UK) and the surrounding area. Given the nature of HVB, the comprehensive eligibility criteria are as follows:

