Participants will be briefly screened for eligibility prior to taking part into the study. They will be randomly allocated to HVB or meditation groups using block randomisation (1:1), stratified by scores on the brief 9-item Imperial Psychedelic Predictor Scale (IPPS), which will be completed shortly after the Consent Form has been signed. Short self-completion questionnaires will be administered to participants ~1 week pre and post the HVB or body scan meditation, along with once immediately after the HVB and meditation. The platform used for questionnaires will be Qualtrics and, where visual analogue scales are used, will contain a scale with 0 (%) on the left and 100 (%) on the right. The single sessions of breathwork and meditation will take place at Little Dippers in Brighton, a naturalistic setting where the facilitator regularly teaches HVB.

Participants will be compensated 5GBP, 10GBP and 15GBP (money) per questionnaire completed (30GBP total but in a phased manner to increase retention). Moreover, participants, regardless of group, will be participating in an active intervention (HVB or body scan meditation) which will be provided free of charge.

Processing and Analysis Plan

Results will be analysed using the software programme *R*. The outcome measures collected on the day of the HVB or meditation will be analysed using simple quantitative analyses (i.e., unpaired t-test or Mann-Whitney U-test depending on distribution of the data), whilst the outcomes ~1-week pre-post will be analysed using repeated-measure analysis of variance (ANOVA) or Friedman's test depending on distribution of the data. Changes on the mental health and wellbeing measures will be correlated with scores on the ASC measures. Simple qualitative content analysis will be used to analyse any responses to open-ended questions of participants' experience of the HVB or meditation.

Ethical considerations

The Brighton and Sussex Medical School Research Governance and Ethics Committee (RGEC) has assessed this project and granted Ethical and Research Governance Approval to proceed (Reference Number: ERA/GF221/9/1).

References

1. Havenith, M. N., Leidenberger, M., Brasanac, J., Corvacho, M., Carmo Figueiredo, I., Schwarz, L., ... & Jungaberle, A. (2025). Decreased CO₂ saturation during circular breathwork supports emergence of altered states of consciousness. *Communications Psychology*, 3(1), 59.

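### If the pre-post scores look non-normal, the planned Friedman's test has no arm term and cannot compare HVB with meditation (Objective 3)

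*Combined protocol and SAP*

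**What the plan says.** Objective 3 under Research Aims/Questions reads "Investigate potential differences on mental health and wellbeing after HVB or a body scan meditation". The Summary states the general purpose: "The study will compare the effects of a single guided HVB session to a single guided body scan meditation session". The design is parallel; under Study type, "participants are randomly assigned to a HVB intervention or body scan meditation".

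Data collection procedures fixes the time points: "The following trait measures will be completed 7-10 days before and 7-10 days after the breathwork and meditation sessions: DASS, SWEMWBS, PROMIS and SFQ". Each of these measures therefore has one pre and one post score per participant. PIQ differs: "the PIQ will be completed 7-10 days after the breathwork and meditation sessions".

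The Processing and Analysis Plan has two testing rules. Same-day outcomes get an "unpaired t-test or Mann-Whitney U-test depending on distribution of the data". For the rest, "whilst the outcomes ~1-week pre-post will be analysed using repeated-measure analysis of variance (ANOVA) or Friedman's test depending on distribution of the data". It names no between-subject factor, interaction, change-score comparison or baseline adjustment for the pre-post outcomes.

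The Sample section supports the sample size with a "between-groups effect size (1.29) on the self-completion depressive symptomology survey, a sample size of 22 is needed".

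**The concern.** Friedman's test is a one-factor, within-subject rank test. In a two-arm trial with one pre and one post score, it asks whether participants as a whole moved up or down. It does not ask whether they moved differently by arm. Running it separately in each arm and comparing the two p-values is not a between-arm test either.

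If the scores are judged non-normal, following the plan gives no result for HVB versus meditation on any of the four measures. A change shared by both arms (regression to the mean, expectancy, or benefit from either session) would give a small p-value. That is correct for time but misleading if reported as the Objective 3 result. The same section already uses a two-sample rank test for same-day outcomes, so the gap is specific to the pre-post rule.

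There are two smaller points. A repeated-measures ANOVA with an arm factor yields time, group and group-by-time terms, and the plan does not say which one is the result. PIQ, which is neither same-day nor pre-post, falls under neither rule.

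**Working it through.** **1. The plan's own figure.** Inputs from the Sample section are effect 1.29, 80% power, alpha 0.05; two-sided testing is assumed. For a two-sample t-test the noncentrality is 1.29 × √(n/2), with 2n − 2 degrees of freedom.

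- n = 10 per arm: 2.885, power 77.9%
- n = 11 per arm: 3.025, power 82.1%
- n = 12 per arm: 3.160, power 85.5%

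The stated total of 22 is reproduced, as a comparison between arms.

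**2. What Friedman's test computes here.** With two time points the statistic reduces to

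Q = (n_up − n_down)² / (n_up + n_down), on 1 df.

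Only the counts of improvers and worseners enter. The identity was confirmed on 1,000 random datasets (largest difference 2 × 10⁻¹⁴).

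**3. Count example (illustrative counts, no ties).** Suppose 18 of 24 improve and 6 worsen: Q = (18 − 6)²/24 = 144/24 = 6.0, p = 0.014.

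| Improvers, HVB / meditation (of 12 each) | Friedman p | Fisher p between arms |
|---|---|---|
| 9 / 9 | 0.014 | 1.00 |
| 12 / 6 | 0.014 | 0.014 |

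For 12/6 the one-tail Fisher probability is C(12,6)/C(24,18) = 924/134,596 = 0.0069, which doubles to 0.014.

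**4. Equal change in both arms (no arm difference).** The setting is 12 per arm and a 0.5 SD shift in each. Pre-post correlation r is assumed to be 0.5 or 0.7, as the documents give none. The SD of change is √(2(1 − r)), that is 1.00 or 0.775. Under normal errors the chance of improving is Φ(0.5/1.00) = 0.691 or Φ(0.5/0.775) = 0.741. At n = 24 Friedman rejects when improvers number at least 17 or at most 7, because 10²/24 = 4.17 exceeds 3.84 and 8²/24 = 2.67 does not. The binomial probabilities are 52.8% and 73.2%. With no change at all, the rejection rate is 6.4%.

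Skewed errors were simulated as standardised lognormal, 30,000 trials per scenario:

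| Errors | Friedman rejects, r = 0.5 / 0.7 |
|---|---|
| Normal | 53% / 73% |
| Skewness 1.8 | 74% / 90% |
| Skewness 6.2 | 98% / 99.7% |

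Between-arm tests reject in 3.4–5.2% of the same trials. Run separately by arm, Friedman is significant in exactly one arm in 23–50% of them (36% / 46% under normal errors).

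**5. A true arm difference.** The two tests address different hypotheses, so these figures show what each would report. They are not a comparison of efficiency.

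| Scenario (normal errors, r = 0.5 / 0.7) | Friedman | Mann-Whitney on change |
|---|---|---|
| 1 SD, only HVB changes | 43% / 57% | 61% / 82% |
| +0.5 / −0.5 SD | under 5% | 60% / 83% |
| 1.29 SD, only HVB changes | 57% / 69% | 82% / 96% |

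The last row takes the plan's 1.29 to be in raw-score SD.

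**6. The ANOVA branch.** With two time points, the group-by-time F equals the squared unpaired t on change scores (3.0485 both ways in a check). For a 1.29 SD effect in HVB only (r = 0.5), group-by-time has about 85% power. The group main effect, which averages in the baseline, has about 42%. With an equal 1.29 SD change in both arms, the time term rejects in essentially every trial. The choice of term therefore decides the answer.

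**The case against.** **Objective 3 is loosely worded.** Objective 1 says versus; Objective 3 could be read as change after either session. That ambiguity is real. The Summary's comparison aim, the randomised design and the between-groups sample-size effect all favour the between-arm reading, and on that reading Friedman fails.

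**The harm is conditional.** It needs scores judged non-normal and, for a false claim, a time p-value reported as an arm comparison. The outcomes are secondary in a self-described small pilot. This stands and limits the severity. It does not supply the missing test: under non-normality no rule compares the arms on these measures.

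**The sample size does not rest on the depression effect alone.** The Sample section also cites the pilot nature of the study and the number of breathworkers per facilitator, and does not say whether 1.29 refers to post scores or to change. This stands. The effect is nevertheless a between-groups one on the kind of outcome this rule covers.

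**An analyst would include group in the ANOVA anyway.** Probably so. Naming the term is a clarification, as is the PIQ rule; neither carries the finding.

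**ANCOVA goes beyond the defect.** True: its advantage is efficiency. It also held its size under strong skew (null rejection within 3.6–5.2% across runs), so a rank fallback is not needed for error control. Switching can lose power: for a 1 SD difference at r = 0.5, ANCOVA against Mann-Whitney is 78% against 72% at skewness 1.8, and 86% against 93% at skewness 6.2. The switch also changes the quantity estimated.

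**Conclusion.** The concern holds. For DASS, SWEMWBS, PROMIS and SFQ, the non-normal branch prescribes a test that carries no information on HVB versus meditation, so it cannot answer Objective 3 on the between-arm reading. This is a stated rule that fails, and it follows from the form of the statistic without any distributional assumption.

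The rejection rates depend on the assumed pre-post correlation (0.5 or 0.7), the assumed shifts and error shapes, and scores without ties; none of these is given in the documents. Within that range, a shared 0.5 SD change gives a significant Friedman result in 53% to 99.7% of trials with no arm difference. The point should be fixed before analysis. It does not affect the primary outcomes, which have two-sample tests.

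**What to change.** Delete Friedman's test and replace the pre-post clause with wording such as:

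> For DASS, SWEMWBS, PROMIS and SFQ, the Objective 3 result is the arm coefficient, with 95% CI, from a linear model of the post-session score on arm and the participant's own pre-session score. If residuals are clearly non-normal, the arms are compared by a Mann-Whitney test on post-minus-pre change, with the Hodges-Lehmann difference and 95% CI. PIQ is compared between arms by the same two-sample tests as the same-day outcomes.

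State in advance what counts as clearly non-normal.

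The minimum repair, which is enough to remove the defect, keeps the repeated-measures ANOVA, names group-by-time as the Objective 3 result and uses the same Mann-Whitney fallback. The ANCOVA form gains some power: for a 1 SD arm difference with normal errors and r = 0.5 / 0.7 / 0.8, it has 75% / 89% / 97% against 65% / 86% / 96% for change scores. If IPPS is added as a covariate, use the form applied in stratification, once the plan states it.

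The cost is a few sentences in the SAP and a few lines of R, with no new data. ANCOVA uses one residual degree of freedom for baseline; the minimum repair uses none.

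### The four pre-post secondary outcomes go to repeated-measures ANOVA or Friedman's test with no baseline covariate; a baseline-adjusted model would be more precise unless the pre-post correlation is about 0.9 or higher

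*Combined protocol and SAP*

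**What the plan says.** The section on data collection procedures lists four trait measures "completed 7-10 days before and 7-10 days after the breathwork and meditation sessions: DASS, SWEMWBS, PROMIS and SFQ". Each participant therefore contributes one pre-session and one post-session score per scale. These scales serve the third research objective, which compares mental health and wellbeing between the two arms.

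Under Processing and Analysis Plan, "the outcomes ~1-week pre-post will be analysed using repeated-measure analysis of variance (ANOVA"), or by Friedman's test if the distribution calls for it. The plan does not say which ANOVA term compares the arms, and it mentions no baseline covariate. Unpaired t-tests or Mann-Whitney tests are kept for the measures taken on the day of the session.

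The Sample section gives the only power statement: "At 80% power with an alpha of 0.05", with a "between-groups effect size (1.29) on the self-completion depressive symptomology survey", "a sample size of 22 is needed, allowing room for potential attrition". The recruitment target is that "24 participants (12 per group) will be recruited". Allocation uses "block randomisation (1:1), stratified by scores on the brief 9-item Imperial Psychedelic Predictor Scale (IPPS").

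**The concern.** With two arms and two time points, the group-by-time F statistic is the square of the t statistic comparing post minus pre between arms. That contrast subtracts the whole baseline score, which fixes the baseline slope at 1. If pre and post SDs are equal, the best slope is r. When r is well below 1, the change score carries baseline noise into the comparison and over-corrects any chance baseline difference. ANCOVA estimates the slope instead, from data the trial already collects.

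At stake is precision on the third objective in a trial of 24 people. There is also a possible mismatch with the power statement. Its effect size concerns depressive symptoms, and the trial's own measure of these, DASS, is assigned to the pre-post analysis and not to an unpaired t-test.

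**Working it through.** **Inputs.** From the Sample section: alpha 0.05, power 80%, effect size 1.29, 22 needed, 24 recruited (12 per arm). Not in the documents, so assumed: two-sided testing, normal data, equal pre and post SDs, r over a range, and d = 0.8 as a more modest effect for illustration.

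**1. The plan's own figure.** For an unpaired two-sided t-test with noncentrality d × √(n/2) and 2n − 2 degrees of freedom, d = 1.29 gives 77.9% power at 10 per arm, 82.1% at 11 and 85.5% at 12. The stated 22 is reproduced.

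**2. The identity.** On one simulated data set, the 2 × 2 group-by-time F and the squared change-score t were both 13.554.

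**3. Precision.** With score variance σ² and n per arm (N = 2n):
- Change-score contrast: variance = 2(1 − r)σ² × 2/n.
- ANCOVA: variance = (1 − r²)σ² × 2/n × [1 + 1/(N − 4)]. The bracket is the average price of chance baseline imbalance.
- Ratio, ANCOVA to change score = (1 + r)/2 × [1 + 1/(N − 4)].

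At N = 24 the bracket is 1 + 1/20 = 1.05. At r = 0.3 the ratio is 0.65 × 1.05 = 0.68. The relative CI width is the square root of the ratio times 2.080/2.074, the t quantiles on 21 and 22 degrees of freedom. Power at d = 0.8 uses d/√(2(1 − r)) for the change score. For ANCOVA it uses residual variance (1 − r²) with 21 degrees of freedom, averaged over chance imbalance.

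| r | Variance ratio | CI width ratio | Power at d = 0.8, change score | Power at d = 0.8, ANCOVA |
|---|---|---|---|---|
| 0.3 | 0.68 | 0.83 | 35% | 48% |
| 0.5 | 0.79 | 0.89 | 47% | 56% |
| 0.7 | 0.89 | 0.95 | 68% | 73% |
| 0.8 | 0.945 | 0.975 | 84% | 86% |
| 0.9 | 1.00 | 1.00 | 99% | 99% |
| 0.95 | 1.02 | 1.015 | near 100% | near 100% |

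Simulation (40,000 trials per cell) agreed to within about 0.01 on the variance ratio and about one percentage point on power. Type I error was about 5% for both methods.

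**4. The plan's effect size under the two tests.** This step assumes that 1.29 is standardised by the SD of scores. The change-score effect is then 1.29/√(2(1 − r)); at r = 0.3 it is 1.29/√1.4 = 1.09.

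| r | Change score, 22 | ANCOVA, 22 | Change score, 24 | ANCOVA, 24 |
|---|---|---|---|---|
| 0.3 | 68% | 83% | 72% | 87% |
| 0.4 | 75% | 86% | 79% | 89% |
| 0.5 | 82% | 90% | 86% | 92% |
| 0.7 | 96% | 97% | 97% | 98% |

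Change-score power drops below 80% at r under about 0.47 with 22 completers, or about 0.42 with 24. At r = 0.3, 80% power needs 30 participants with the change score and 22 with ANCOVA. If 1.29 is instead a change-score effect, the change-score test has 82% at 22 whatever r is.

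**The case against.** The planned ANOVA, tested through its interaction, is a valid analysis: it is unbiased over randomisation and holds its type I error. These are four secondary outcomes in a self-described small pilot. The scales are called trait measures and are taken about two to three weeks apart, so r could be high; at r = 0.8 the gain at d = 0.8 is only about two points of power. All of this stands, and it limits the point to efficiency.

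Two stronger readings are tempting and are not supported.

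- A reader might infer that the trial is underpowered for depressive symptoms. The documents do not say how 1.29 was standardised, and one of the two possibilities leaves no shortfall. Even on the other, power is lost only at lower r, and ANCOVA is not the only way to keep it. A follow-up-only t-test also has 82% at 22, while ANCOVA itself has 79.8% at 22 when r = 0.
- A reader might infer that ANCOVA is free and never loses. It uses one degree of freedom. At this sample size the methods tie near r = 0.9, and at r = 0.95 the ANCOVA interval is 1-2% wider.

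It is also fair to object that the plan does not name the interaction, so equating its test with a change-score t-test grants it the better reading. Testing the arm main effect averaged over both time points would do worse: about 42% power at 24 participants, r = 0.5 and d = 1.29. That is a reason to name the contrast.

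**Conclusion.** The point holds as a cheap improvement to the secondary analyses. At 12 per arm, baseline-adjusted ANCOVA narrows the 95% CI by about 17% at r = 0.3, 11% at 0.5, 5% at 0.7 and 3% at 0.8, with a negligible loss above about 0.9. This rests on normal data and equal SDs; r is not given, hence the range.

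The power remark is conditional. The change-score contrast misses the stated 80% only if 1.29 is on the score scale and r is under about 0.47 (22 completers) or 0.42 (24).

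The non-parametric branch has a separate gap. Friedman's test ranks scores within participants and has no between-arm factor, so it cannot answer the third objective. The primary outcomes (5D-ASC, MEQ, EBI) are measured only after the session, have no baseline and are unaffected.

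**What to change.** In Processing and Analysis Plan, for DASS, SWEMWBS, PROMIS and SFQ:

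- Replace repeated-measures ANOVA with a linear model of the score 7-10 days after the session on arm and the same scale's pre-session score. The IPPS stratification factor may be added.
- Report the adjusted HVB-minus-meditation difference with its 95% CI.
- Where the data are clearly non-normal, replace Friedman's test with a baseline-adjusted comparison of arms, for example ANCOVA on ranks or a permutation test of the ANCOVA arm term.
- In the Sample section, state whether 1.29 is standardised by the SD of scores or of change.

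The cost is a few sentences of text, about one line of R per outcome for the linear model, and one degree of freedom for the baseline covariate. No new data or participants are needed.
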